## 6 RESEARCH QUESTION AND OBJECTIVES

### 6.1 Primary Objective

To assess if the odds of JoRRP are lower among children whose biologic mothers were fully vaccinated with GARDASIL/GARDASIL 9 at least one year prior to delivery versus unvaccinated mothers.\*

\* In case-control studies, the odds (likelihood) of exposure are typically assessed among cases of a disease and compared with controls. However, given that the odds ratio is the same regardless of how it is defined in terms of marginal probabilities, i.e., probability of exposure given disease or probability of disease given exposure are statistically equivalent, we have chosen to express it as the latter (probability of disease given exposure) to provide a measure of the protective effect of vaccination against JoRRP. Additionally, given the rare outcome of JoRRP and the use of incidence density sampling, odds ratio estimates will be interpreted as the corresponding relative risks.

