## 7 RESEARCH METHODS

### 7.1 Study Design

#### Nested case-control study (primary objective)

**Setting:** Sweden, Norway, and Denmark.

In 2006, the U.S. Food and Drug Administration and European Medicines Agency approved the use of GARDASIL. National HPV vaccination programs in Scandinavian countries (Denmark, Norway, and Sweden) were instituted in subsequent years (~2008 or afterward) for young female adolescents, with catch-up vaccination programs for cohorts of older adolescents, teens, and/or young women in Denmark and Sweden. In Denmark, GARDASIL

PRODUCT: V501/V503	PROTOCOL/AMENDMENT VERSION NO.: V503-095-00-v3
REVOPS ID NO: NIS102781	CORE DRC APPROVAL DATE: 18MAR2024
EPIDEMIOLOGY NO.(PE STUDIES ONLY): 08039.022	

was used from October 2008 to February 2016, Cervarix (recombinant HPV bivalent [types 16 and 18] vaccine) from February 2016 to November 2017, and GARDASIL 9 since November 2017 (currently in use). The national HPV vaccination program targeting girls aged 12 years (primary cohort) was introduced in 2009, with fully subsidized catch-up vaccination for girls 13-15 years of age available since 2008, and girls/women up to 27 years of age since 2012. In Sweden, national HPV vaccination program using GARDASIL was introduced in 2010, with large-scale vaccination and high coverage achieved in 2012, with GARDASIL 9 being used since 2020. Fully subsidized catch-up vaccination for girls aged 13-17 years has been available in Sweden since 2012, and partially subsidized for the same age group since 2007. In Norway, the HPV vaccination program was initiated in 2009, in which girls approximately 12 years of age were offered GARDASIL in a three-dose schedule (until 2017). Catch-up vaccination was offered in Norway during the period 2016–2019 to women born between 1991 and 1996. Since 2017, Cervarix has been used in Norway. In 2015, a 2-dose schedule (with doses administered at 0 and 6 months) was recommended for females  $\leq 14$  years of age in Denmark and Sweden.

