**Controls:** For each case of JoRRP, up to 100 control subjects free of this diagnosis, at the time of the case’s diagnosis, will be identified from the cohort. As the number of controls per case increases beyond 4, improvement in statistical power diminishes [30]. However, given that data for additional controls are readily available in this database study, effort will be made to identify 100 controls per case. Cases and controls will be matched as closely as possible on age of mother (+/- 1 year), sex of child, and region where case was diagnosed. By design of the study (nested case-control), cases and controls will also be matched on calendar year of diagnosis. Controls will be selected from the population at risk at the point in time when a case is diagnosed with JoRRP. All controls who meet the matching criteria will be assigned a random number using SAS statistical software (SAS Institute Inc, Cary, NC) procedures. Then, 100 controls for each case will be selected at random from the pool of eligible controls. Controls will be assigned the same index date (date of birth) as the case to which they are matched. [Figure 1] provides an example of case/control subject selection nested within population-based cohort in this study.

**Exposure assessment:** The exposure of interest is GARDASIL or GARDASIL 9 vaccination in mother, one year prior to delivery, for each case and matched controls (see Figure 1 below).

PRODUCT: V501/V503	PROTOCOL/AMENDMENT VERSION NO.: V503-095-00-v3
REVOPS ID NO: NIS102781	CORE DRC APPROVAL DATE: 18MAR2024
EPIDEMIOLOGY NO.(PE STUDIES ONLY): 08039.022	

Exposure will be defined in 2 ways:

1. Exposure in primary objective: Fully vaccinated with GARDASIL/GARDASIL 9 (yes/no). A female/mother who received 3 doses (or 2 doses administered at 0 and 6-12 months if <15 years of age) of GARDASIL/GARDASIL 9 one year prior to delivery will be classified as exposed.
2. Exposure in sensitivity analysis: GARDASIL/GARDASIL 9 vaccination (yes/no). A female/mother who received at least one dose of GARDASIL/GARDASIL 9 one year prior to delivery will be classified as exposed.

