### Cohort entry (2008-2020)

[figure not shown]

Figure 1 Example of Case/Control Subject Selection and Exposure Assessment, Nested Within Population-Based Cohort in this Study.

Subject 1 is classified as a case without maternal history of exposure to GARDASIL/GARDASIL 9  $\geq 1$  year prior to delivery, and subject 2 is an eligible matched control with maternal history of exposure to GARDASIL/GARDASIL 9  $\geq 1$  year prior to delivery.

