### 7.2.2 Exclusion Criteria

A flow diagram to highlight the exclusion criteria is shown in [Figure 2](#) below.

- Children whose mother immigrated to Sweden, Denmark, or Norway both after 2006 and after age 9 years will be excluded as vaccination exposure status is unknown.
- Since the hypothesis of HPV transmission is that it occurs in mothers giving birth to biological children, adopted children will be excluded from the analysis as vaccination status of the actual, biological mother will be missing.
- Children whose mother received the bivalent vaccine Cervarix will be excluded since it provides no effectiveness against the causative HPV types (6 and 11) in RRP.
- Any child (case or control subject) who previously received any HPV vaccine will be excluded from analysis.

[figure not shown]

Figure 2 Flow Diagram Describing Steps to be Used in Creation of Data Set for Each Country, Based on Listed Inclusion/Exclusion Criteria

PRODUCT: V501/V503	PROTOCOL/AMENDMENT VERSION NO.: V503-095-00-v3
REVOPS ID NO: NIS102781	CORE DRC APPROVAL DATE: 18MAR2024
EPIDEMIOLOGY NO.(PE STUDIES ONLY): 08039.022	

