## Annex 2 TABLE AND FIGURE SHELLS FOR RRP STUDY (PRIMARY OBJECTIVE)

Table 2 Characteristics of Study Population, JoRRP Cases, and Control Subjects (prepared separately for each country)

	Study population, No. (%)	JoRRP cases, No. (%)	Controls, No. (%)
Age of child , years, mean (SD)			
Age of mother at delivery , years, mean (SD)			
Highest level of education achieved by mother*			
Low			
Medium			
High			
Missing			
Highest annual household family income level‡			
Low			
Medium			
High			
Missing			
Mother's country of birth			
Current country of residence			
Other country			
Missing			
Method of delivery			
Vaginal			
Cesarean			
Missing			
Maternal history of EGW			
Yes			
No			
Missing			
Maternal smoking status at first prenatal visit			
Yes			
No			
Missing			

EGW = external genital warts; JoRRP = juvenile-onset recurrent respiratory papillomatosis; SD = standard deviation

\*Education level of mother at index date.

‡Based on average level between 2006 (the start year of HPV vaccination) and the index date.

PRODUCT: V501/V503	PROTOCOL/AMENDMENT VERSION NO.: V503-095-00-v3
REVOPS ID NO: NIS102781	CORE DRC APPROVAL DATE: 18MAR2024
EPIDEMIOLOGY NO.(PE STUDIES ONLY): 08039.022	

Table 3 Number of Cases and Odds Ratio for Recurrent Respiratory Papillomatosis (RRP) by GARDASIL/GARDASIL 9 Vaccination Status, 2008-2020

GARDASIL/ GARDASIL 9 vaccination status	JoRRP (ICD-10 code: D14.1)			
	No. of cases 	No. of controls 	Crude OR (95% CI)	Adjusted OR  (95% CI)
Fully Vaccinated 			Ref.	Ref.
Unvaccinated				

*CI = confidence interval; HPV = human papillomavirus; ICD-10 = international classification of disease, 10th modification; JoRRP = juvenile-onset recurrent respiratory papillomatosis; OR = odds ratio; Ref. = reference.*

 All study participants who acquired a first diagnosis of D14.1 before age 10 years and appropriate topography/morphology code (if available from pathology/cancer registry).

 Up to 100 controls matched on age of mother, sex of subject, and region of diagnosis.

 Adjustment factors considered for inclusion include maternal education level, family income level, maternal smoking status, mother's country of birth, and method of delivery.

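### The yes/no coding of primary exposure conflicts with the stated unvaccinated comparator, and the Cervarix exclusion has no time limit, so it can act on doses given after birth

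*Protocol*

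**What the plan says.** **Comparator.** Section 6.1 compares children of mothers "fully vaccinated with GARDASIL/GARDASIL 9 at least one year prior to delivery versus unvaccinated mothers". Section 7.5 states the same contrast as the hypothesis to be powered. The Table 3 shell in Annex 2 has two rows, fully vaccinated and "Unvaccinated", and its footnotes define only the first.

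**Exposure rule.** Section 7.1 gives "Exposure in primary objective: Fully vaccinated with GARDASIL/GARDASIL 9 (yes/no" and then says which mothers count as exposed: those with the complete series one year before delivery. It does not say who belongs in the no class. The Figure 1 legend points to everyone else: "Subject 1 is classified as a case without maternal history of exposure to GARDASIL/GARDASIL 9", with the same one-year limit attached.

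**Sensitivity exposure.** "A female/mother who received at least one dose of GARDASIL/GARDASIL 9 one year prior to delivery will be classified as exposed".

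**Cervarix.** Section 7.2.2 says: "Children whose mother received the bivalent vaccine Cervarix will be excluded since it provides no effectiveness against the causative HPV types". Section 7.8.1 repeats this and extends it to mothers who also had GARDASIL or GARDASIL 9. Neither gives a date limit. Section 7.1 dates Cervarix use in Denmark to February 2016 to November 2017 and adds: "Since 2017, Cervarix has been used in Norway". Eligible births start in 2008, and the index date is the date of birth.

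**The concern.** The objective names two groups, but mothers fall into at least three: no dose before delivery, a full series at least a year before, and something in between. The in-between mothers have an incomplete series, or a series whose last dose falls inside the final year before delivery. A yes/no variable puts them in the no class, and no exclusion in 7.2.2 or 7.8.1 removes them. If they have some protection, the unexposed group carries less disease than a truly unvaccinated one, and the odds ratio shrinks. An analyst who instead follows the word unvaccinated in section 6.1 and Table 3 would drop them. The two readings give different estimates from the same data, and section 7.5 judges the estimate against a point threshold of 3.0 as well as a lower confidence bound of 1.33.

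The Cervarix rule raises a different problem. Exposure is fixed at delivery, but this exclusion can depend on something the mother does years later. It discards mothers who were validly unexposed at delivery, and it conditions on an event after the index date.

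**Working it through.** **1. The plan's own figure.** Section 7.5 gives 94% power (200 cases, 100 controls per case, 5% coverage, odds ratio 3.0, lower 95% bound above 1.33) and 92% with 10 controls per case. Simulating an unmatched 2×2 table with a Wald interval, 5% exposure in controls and an exposure that triples the odds, gives 0.93 and 0.91. The figures are reproduced in that direction. Whether that is the right direction for a protective vaccine is a separate question; the dilution in steps 3 and 4 does not depend on it.

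**2. Who is coded how**

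| Mother's status at delivery | Section 6.1 / Table 3 label | Section 7.1 yes/no rule | At-least-one-dose sensitivity analysis |
|---|---|---|---|
| Full series, at least one year before | fully vaccinated | yes | yes |
| Incomplete series, at least one dose a year or more before | neither | no | yes |
| Series completed inside the last year, first dose earlier | neither | no | yes |
| All doses inside the last year | neither | no | no |
| First dose after delivery | unvaccinated at delivery | no | no |
| Never vaccinated | unvaccinated | no | no |

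The fifth row is correctly unexposed for that delivery. Rows two to four are the problem. The sensitivity analysis moves rows two and three into the exposed group and leaves row four in the unexposed group. Under the yes/no rule, neither planned analysis compares the full series with zero doses.

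**3. Size of the dilution.** Let c be full coverage, q the share of mothers in rows two to four, and r their odds of JoRRP relative to never-vaccinated mothers. The outcome is rare, so

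OR(mixed) = OR(true) × [(1 − c − q) + q·r] / (1 − c).

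Coverage of 5% to 10% and the odds ratio of 3.0 come from section 7.5. The protocol gives neither q nor r, so both are assumed: q from 1% to 10%; r of 1/3 (as good as the full series, which section 7.1 allows for one dose), 1/2, or 1 (no protection).

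Worked case: c = 0.05, q = 0.01, r = 1/3 gives 3 × (0.94 + 0.0033)/0.95 = 2.98.

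| c | r | q = 1% | 2% | 5% | 10% |
|---|---|---|---|---|---|
| 5% | 1/3 | 2.98 | 2.96 | 2.89 | 2.79 |
| 5% | 1/2 | 2.98 | 2.97 | 2.92 | 2.84 |
| 10% | 1/3 | 2.98 | 2.96 | 2.89 | 2.78 |
| 10% | 1/2 | 2.98 | 2.97 | 2.92 | 2.83 |
| either | 1 | 3.00 | 3.00 | 3.00 | 3.00 |

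As vaccine effectiveness (1 − 1/OR), the fall is from 66.7% to 64.0% at worst (1 − 1/2.78).

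Where coverage within a risk set is higher, the dilution grows. As an illustration with assumed coverages, with q at one fifth of c and r = 1/3, c = 30% gives 3 × (0.64 + 0.02)/0.70 = 2.83, and c = 50% gives 3 × (0.40 + 0.033)/0.50 = 2.60.

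**4. Effect on the success criterion.** With a true odds ratio of exactly 3.0, about half of all estimates fall below 3.0 with no dilution at all. The standard error of the log odds ratio (200 cases, 20,000 controls, 5% coverage) is 0.21 if exposure triples the odds and 0.54 if it divides them by three. At r = 1/3 the extra chance of falling below 3.0 is Φ[ln(3.0/OR mixed)/SE] − 0.5. For 2.98 (q = 1%) that is 0.5 to 1.3 percentage points; for 2.79 (q = 10%) it is about 5 to 14 points. The closed-form power for the 1.33 bound, in the direction that reproduces Table 1, goes from 97.4% to 95.7% (q = 5%) and 93.3% (q = 10%); this formula runs higher than the simulation, so only the change is of interest.

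**5. Cervarix.** Take a Norwegian child born in 2010 to a mother with no HPV vaccine before delivery. If she received Cervarix in 2017, when the child was 7 and still in the 0 to 9 age window, the child is excluded. The dose may even follow the child's diagnosis. If later uptake is unrelated to JoRRP within risk sets, cases and controls lose the same fraction of unexposed children and the odds ratio is unchanged; what is lost is data. If uptake is related, the odds ratio is biased in a direction set by that relation. The protocol has no figure for either.

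**The case against.** The strongest reply is that the protocol names its comparator as unvaccinated in several places, so an analyst could simply leave the intermediate mothers out; the gap is then a missing definition of the kind often left to an analysis plan. This stands in part: the text does not settle that these mothers are in the unexposed group. But section 7.1 does state a rule, and applied as written it produces the mixed group. That is a conflict inside the protocol.

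The at-least-one-dose analysis is prespecified and covers part of the intermediate group. True, but it answers a different question and leaves in place the mothers whose doses all fell in the last year.

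A reader might infer from the expected values below 3.0 that the study will fail its own criterion. The documents do not support that. The shift is in an expectation, is small against the sampling error, and at 5% coverage may be as little as 3.00 to 2.98. The larger figures for 30% and 50% coverage rest on assumed coverages, and section 7.3.1 says that few cases have arisen among children of mothers born from 1992 on.

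A reader might also infer that a JoRRP diagnosis prompts Cervarix vaccination, so that the exclusion removes cases preferentially. Nothing in the protocol says so. Norway's catch-up was offered by maternal birth year, its product is not named, and risk sets are matched on maternal age and region. Section 7.1 also speaks of comparing vaccination status before delivery, which suggests that a pre-delivery limit was intended. The exclusion rules as written do not contain it.

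**Conclusion.** Both parts hold as defects of definition. The primary exposure rule and the stated comparator disagree about mothers who are partly vaccinated or vaccinated within a year of delivery, and nothing in the protocol resolves it. Under the literal rule the bias is towards 1 and modest: a true odds ratio of 3.0 is expected at about 2.8 to 3.0 for 5% to 10% coverage, given assumed intermediate shares of 1% to 10% and relative odds from 1/3 to 1. It disappears if these mothers have no protection and grows in risk sets with higher coverage. It does not overturn the power statement.

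The undated Cervarix exclusion conditions on a post-index event and discards valid unexposed mothers. Whether it biases the odds ratio depends on a relation that the protocol does not describe, and its size cannot be estimated. The point should be corrected before vaccination status is analysed; it is not a reason to doubt the design.

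**What to change.** In sections 6.1, 7.1, 7.3.1 and Table 3:

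- Define the unexposed group as mothers with zero doses of any HPV vaccine before delivery.
- Keep the exposed group as the protocol defines it, at least one year before delivery.
- Put mothers with an incomplete series, or with doses inside the year before delivery, in a third category. Give it its own term in the conditional logistic model or exclude it from the primary contrast, and say which. Add a row for it to Table 3.

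In sections 7.2.2 and 7.8.1, limit the Cervarix exclusion to doses given before delivery.

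Dose dates are already among the variables requested from the registries in section 7.4, so the cost is protocol wording and one derived variable. A few mothers leave the unexposed group, and some now lost to the Cervarix rule return to it.

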### Cohort entry (2008-2020)

[figure not shown]

Figure 1 Example of Case/Control Subject Selection and Exposure Assessment, Nested Within Population-Based Cohort in this Study.

Subject 1 is classified as a case without maternal history of exposure to GARDASIL/GARDASIL 9  $\geq 1$  year prior to delivery, and subject 2 is an eligible matched control with maternal history of exposure to GARDASIL/GARDASIL 9  $\geq 1$  year prior to delivery.

## 7.2 Setting

The study population is identified using the Total Population Registry in each of the Nordic countries, for information on birth year, migration status, and date of death in each of the respective countries. The registers have full coverage of the Swedish, Danish, and Norwegian populations.

The study population includes male/female children (0-9 years of age) from Sweden, Norway, and Denmark during time period 2008 to 2020, whose mother had the opportunity to be fully vaccinated with GARDASIL/GARDASIL 9 at least one year prior to delivery, i.e., birth cohorts 2008-2020.

PRODUCT: V501/V503	PROTOCOL/AMENDMENT VERSION NO.: V503-095-00-v3
REVOPS ID NO: NIS102781	CORE DRC APPROVAL DATE: 18MAR2024
EPIDEMIOLOGY NO.(PE STUDIES ONLY): 08039.022	

### 7.2.1 Inclusion Criteria

- Birth cohorts 2008 to 2020
- The study subject (child) must be born and resident in Sweden, Denmark or Norway as defined through the Total Population Registry for their entire life, to ensure incident JoRRP case is truly new onset.
- The study subject must be between 0 to 9 years of age (due to direct HPV-vaccine receipt at ages 10-12 years) through school-based programs in some countries.

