##### Central Population Registry

- date of birth (subject/mother)
- gender
- migration status (subject/mother)
- date of death, if applicable

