## 7.10 Limitations of the Research Methods

This is a register-based study which relies on the use of a proxy codes rather than medical records. It is thus limited in terms of density of data, such that there is not access to all medical details for each case. On the other hand, there is excellent systematicity, and generalizability due to the structural nature of the register sampling frame. There is also no available explicit information on certain lifestyle factors of the mother, such as sexual behavior; however, there are several proxy variables that may serve to adjust for potential confounding (Annex 1). Additionally, with use of registry data from three different countries, some variables may need to be adapted to be able to combine information as it is not identical in all registers. This will be achieved via development of a common data model, involving collaboration between all Nordic country investigators.

Given that the main cause of JoRRP globally is infection with HPV type 6 or 11, results are expected to be generalizable. With the proposed study population design, there is restriction

PRODUCT: V501/V503	PROTOCOL/AMENDMENT VERSION NO.: V503-095-00-v3
REVOPS ID NO: NIS102781	CORE DRC APPROVAL DATE: 18MAR2024
EPIDEMIOLOGY NO.(PE STUDIES ONLY): 08039.022	

in analytical format; as having access to the full baseline cohort will yield many technical advantages. The risk for misclassification of exposure to vaccination is minimized through substantial knowledge and experience utilizing vaccination registries by investigators in each of the respective countries. Nonetheless there is a small but existing risk of non-differential misclassification of the outcome. Generalizability is maximized through the population-based sampling frame and allowing all eligible study participants who are alive and reside in Sweden, Denmark, and Norway at the appropriate time to enter. Also, in recent years, especially the post-vaccination introduction era, Sweden, Denmark, and Norway have experienced high immigration, which may further increase generalizability of study results.

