### 7.11 Methods to Minimize Bias

A register-based proxy for definition of outcome (JoRRP) will be used, i.e., ICD-10 code D14.1, which in all countries (Sweden, Denmark, and Norway) is used to register the disease category “benign tumor of the larynx”. Where possible, appropriate topography/morphology codes for RRP will also be applied to further increase outcome specificity. Additionally, in sensitivity analyses, diagnostic and treatment codes described above will be applied to also improve specificity in settings where topography/morphology codes cannot be accessed in the pathology or cancer registry. Given that granulomas of the larynx are largely occurring in middle-age, male smokers, it is suggested that benign tumors of the larynx, other than HPV-associated papilloma, among children (ages 0-9 years), will be very rare. If a misclassification of outcome due to using D14.1 would sometimes occur, it will likely lead to bias towards the null, which means that if vaccine effectiveness against JoRRP is observed, the true effect is likely greater.

Given the rarity of JoRRP, and the strong registration of Swedish, Danish, and Norwegian healthcare, it is believed that virtually all cases of JoRRP will be identified by the above algorithm. The risk that a control selected at random from the underlying population is actually a false negative, i.e., a missed case of RRP, should be negligible.

All subjects whose mother immigrated to Sweden, Denmark, or Norway (after age 9) will be excluded, to ensure there is no misclassification of exposure, which removes the risk that mothers who have received HPV vaccination outside of their country are mis-classified as non-vaccinated. Also, to ensure that prevalent cases of JoRRP are excluded, subjects (children) born or ever living in another country will not be eligible, as follow-up in registries may be insufficient to determine if incident case is truly new onset.

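### The child residence criterion has no end date, so read literally it drops incident cases and valid controls who move abroad after the risk-set date

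*Protocol*

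**What the plan says.** Section 7.2.1 requires that the child "must be born and resident in Sweden, Denmark or Norway as defined through the Total Population Registry for their entire life". The reason follows in the same bullet: "to ensure incident JoRRP case is truly new onset". Section 7.11 restates the rule as an exclusion, "subjects (children) born or ever living in another country will not be eligible", and again justifies it by the need to tell new-onset from prevalent disease. Neither sentence says when the residence test stops.

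The sampling scheme is tied to a different time point. Section 7.1 states: "Controls will be selected from the population at risk at the point in time when a case is diagnosed with JoRRP". Section 7.3.2 calls this incidence density sampling, and section 7.8.1 relies on it to interpret the odds ratio as a hazard ratio.

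The index date does not supply the missing limit, because section 7.1 sets it at birth: "Controls will be assigned the same index date (date of birth) as the case to which they are matched". The nearest softer wording is in section 7.10, which speaks of "allowing all eligible study participants who are alive and reside in Sweden, Denmark, and Norway at the appropriate time to enter". It does not define that time, and it applies to participants who are already eligible.

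**The concern.** Under incidence density sampling, whether a child belongs to a risk set is settled by what is known at the case's diagnosis date. A rule that looks at residence over the whole life, or at ever having lived abroad, uses information from after that date.

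Two kinds of children are then lost. One is a child diagnosed at age 3, resident since birth, who moves abroad at age 7; the diagnosis was incident, yet the child fails the criterion. The other is a child who was resident and free of disease when a case was diagnosed and who later emigrates; that child was a valid control.

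Three things are at stake:

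- **Case count.** It decides whether the primary analysis goes ahead (7.5).
- **Selection.** Inclusion would depend on later family behaviour.
- **Consistency.** Section 7.6 has each country prepare its variables before data go to Denmark, with its own team and software. A criterion without an end date could be programmed in three ways and then pooled in one model.

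**Working it through.** **1. Purpose against rule.** Showing that a diagnosis is new onset needs an unbroken registry history from birth to diagnosis. Residence after diagnosis adds nothing to it. The rule as worded is therefore wider than its stated reason, and it does not use the date at which 7.1, 7.3.2 and 7.8.1 fix control selection.

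**2. Cases lost.** The protocol gives no emigration rate for children. Assume a yearly rate r of 0.3% to 1.0% and five years of registry time after diagnosis. The share lost is 1 − (1 − r)^5.

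- r = 0.003: 1 − 0.997^5 = 1.5%, or 3 of 200 cases.
- r = 0.010: 1 − 0.990^5 = 4.9%, or about 10 of 200 cases.

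The 200 is the expected total in section 7.5.

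**3. Reproducing the stated power.** Section 7.5 gives 94% for 200 cases, 100 controls per case, 5% coverage, an odds ratio of 3.0 and a lower 95% confidence bound above 1.33. The check was a simulation of an unmatched 2×2 table (200,000 replicates) with a Wald interval on the log odds ratio. Control exposure is 5%. Case exposure odds are 3 × 0.05/0.95 = 0.158, so case exposure is 0.158/1.158 = 13.6%.

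| Cases | Controls per case | Protocol | Simulated |
|---|---|---|---|
| 200 | 100 | 94% | 93.4% |
| 200 | 10 | 92% | 90.7% |
| 125 | 100 | 80% | 80.2% |
| 100 | 100 | 72% | 72.2% |
| 100 | 10 | 68% | 66.3% |

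All agree within 2 points. The closed-form Wald formula gives 97.4% for the first row and does not match, so the simulation is used below. This reproduces the protocol's figure on its own basis, with higher odds in the 5% exposed group. Whether that basis suits a protective vaccine is a separate question.

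**4. Power after losing cases** (100 controls per case)

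| Share lost (assumed) | Cases left | Simulated power |
|---|---|---|
| 0% | 200 | 93.4% |
| 1% | 198 | 93.2% |
| 2% | 196 | 93.1% |
| 5% | 190 | 92.3% |
| 10% | 180 | 91.1% |

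Over the 1.5% to 5% range the cost is at most 93.4 − 92.3 = 1.1 points. Even 10% lost costs 2.3 points. Losing controls matters less still: in the protocol's own figures, going from 100 controls per case to 10 costs only 2 points.

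**5. Bias.** Let k be the probability of staying eligible after the risk-set date. The vaccinated-versus-unvaccinated odds ratio is multiplied by (k for vaccinated cases / k for unvaccinated cases) ÷ (k for vaccinated controls / k for unvaccinated controls). All values below are assumptions.

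- Same retention in all four groups (0.97): multiplier 1.00.
- Retention differs by vaccination, similarly in cases and controls: (0.98/0.96) ÷ (0.97/0.95) = 1.00.
- Differs jointly: (0.99/0.98) ÷ (0.97/0.93) = 0.97.
- Differs jointly, more extreme: (1.00/0.99) ÷ (0.96/0.90) = 0.95.

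A difference by vaccination alone does not bias the estimate. It must also differ by case status.

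**The case against.** The best defence is that a look-back was meant. Both sections justify the rule by new onset, which concerns history before diagnosis. Controls are chosen at the case's diagnosis date, and section 7.10 refers to residence at a suitable time. On that reading, a lifetime means life up to selection. Figures 1 and 2 are not visible in the text available here and might carry the date. This defence has force: the protocol cannot be said to have chosen to condition on the future. What remains is that two sections state the rule without a limit, the second in terms of ever having lived abroad, and no visible text supplies one.

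A second objection is that the consequence is small and the emigration rates are assumed. That stands and limits the weight of the point.

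A reader might draw two stronger conclusions that the protocol does not support:

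- **That the child-vaccination exclusion has the same fault and removes a large share of children.** Section 7.2.2 says: "Any child (case or control subject) who previously received any HPV vaccine will be excluded from analysis". The ordinary meaning is before diagnosis or selection. Section 7.2.1 limits subjects to ages 0 to 9 precisely because direct vaccination comes at 10 to 12. A large loss follows only if the exclusion is judged at data cut-off, and it needs an uptake figure that the protocol does not give.
- **That the odds ratio is biased.** This needs later emigration to depend jointly on case status and maternal vaccination. Maternal origin is linked to vaccine uptake in Annex 1, but nothing shows that the dependence differs between cases and controls. Maternal education and family income are planned adjustments, and mother's country of birth is a candidate.

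**Conclusion.** The point holds as a fault of wording with a small expected effect. Sections 7.2.1 and 7.11 state the child residence rule without an end date. Followed literally, it removes incident cases and valid controls for emigration after the risk-set date, exceeds its own purpose and conflicts with the sampling design.

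Under assumed emigration of 0.3% to 1.0% per year for five years, the loss is about 1.5% to 5% of cases (3 to 10 of 200), or roughly 0 to 1 power point on the protocol's own basis. Bias in the odds ratio is possible only under joint dependence; the illustrative values that create it move the estimate by a factor of 0.95 to 0.97. The case for correcting it is that the text states a rule at odds with the design, three national teams must program it, and the correction is nearly free.

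**What to change.** In sections 7.2.1 and 7.11, replace the open-ended residence wording with this: the child must be born in the country and continuously resident there from birth to the date of the case's diagnosis; for a control, to the diagnosis date of the matched case. Add that later emigration does not affect eligibility. This serves the new-onset purpose in full and agrees with 7.1, 7.3.2 and 7.8.1. For consistency, the same date can be named in the child-vaccination exclusion in 7.2.2; that is a clarification, not a correction.

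The cost is an amendment to two sentences and a date condition in each country's cohort program. One check is needed first. Section 7.4 lists migration status, not migration dates, for all three countries, and the Norwegian entry does not say whether it covers child, mother or both. Each country should confirm that dated migration records for the child are extracted; if they are not, the data request must be extended.
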